6. STUDY INTERVENTION

6.1. Identity of Test Articles

The following contact lenses will be used in this study:

Clinical Study Protocol

Johnson & Johnson Vision Care, Inc.

Table 1: Test Articles

	Test	Control
Name and Description	Acuvue® Oasys MAX 1-Day	Dailies Total 1
Manufacturer	Johnson & Johnson Vision	Alcon
	Marketed Product	Marketed Product
Lens Material	senofilcon A	delefilcon A
Nominal Base Curve @ 22°C	8.5 mm	8.5 mm
Nominal Diameter @ 22°C	14.3 mm	14.1 mm
Nominal Distance Powers (D)	-1.00 to -6.00	-1.00 to -6.00
Oxygen Permeability (Dk, edge corrected)	103	140
Wear Schedule in Current Study	Daily disposable	Daily disposable
Replacement Frequency	Daily	Daily
Packaging Form (vial, blister, etc.)	Blister	Blister

It is estimated that if 10 subjects are enrolled and use up to 42 lenses per subject, a total of approximately 420 lenses will be used.

6.2. Ancillary Supplies/Products

The following solutions will be used in this study:

Table 2: Ancillary Supplies (locally sourced by research site)

	Solution	Supplies
Solution Name/Description	Saline pods	Fluorescein Strips
Manufacturer	Any Sponsor approved manufacturer of sterile, preservative free, single use saline (0.9% w/v sodium chloride solution)	Contacare Ophthalmics and Diagnostics (or Alternative Sponsor approved product)
Preservative	None	None
Other distinguishing items (dye, packaging, approval status, etc.)	CE marked	CE marked

Clinical Study Protocol

Johnson & Johnson Vision Care, Inc.

6.3. Administration of Test Articles

Test articles will be dispensed to subjects meeting all eligibility requirements, including any dispensing requirements set forth in this clinical protocol. Subjects will be dispensed an adequate supply of test articles to complete the study. Lost or damaged test articles may be replaced at the discretion of the Investigator and/or the Sponsor.

6.4. Packaging and Labeling

The test articles will be packaged in blisters as the primary packaging. The test article will be over-labelled to mask the subjects to the identity of the lens. The test articles will be in investigational cartons sealed with a tamper evident seal as the secondary packaging form. The sample study label is shown below:

Primary Packaging:

For Use in Clinical Study CR-6495 Only Not For Sale Product Conforms with CE Mark Requirements
Contents: One contact lens in solution.
 
LOT C1T602 SPH -1.00 EXP 2027/01/01 RC H

Secondary packaging:

Sponsored By/Parrainé par: Johnson & Johnson Vision Care, Inc. [name]
Contents/Contenu: Contact Lenses in Solution Lentilles cornéennes dans une solution

6.5. Storage Conditions

Test articles will be maintained at ambient temperatures at the clinical site. Test articles must be kept under secure conditions.

Clinical Study Protocol

Johnson & Johnson Vision Care, Inc.

6.6. Collection and Storage of Samples

When possible, any lens or test article associated with an Adverse Event and/or a Product Quality Complaint must be retained and stored in a glass vial with moderate solution pending directions from the Sponsor for potential return to JJVC.

6.7. Accountability of Test Articles

JJVC will provide the Investigator with sufficient quantities of study articles and supplies to complete the investigation. The Investigator is asked to retain all lens shipment documentation for the test article accountability records.

Test articles must be kept in a locked storage cabinet, accessible only to those assigned by the Investigator for dispensing. The Investigator may delegate this activity to authorized study site personnel listed on the Site Delegation Log. All test articles must be accounted. This includes:

1. What was dispensed for the subject for trial fitting, to wear out of the office, or issued for the subject to replace appropriately between visits.
2. What was returned to the Investigator unused, including expired or malfunctioning product.
3. The number and reason for unplanned replacements.

The Investigator will collect all unused test articles from the subjects at the end of the subject's participation. Subject returned unused test articles must be separated from the clinical study inventory of un-dispensed test articles and must be labeled with the subject number and date of return. Following final reconciliation of test articles by the monitor, the test articles may be retained by the Investigator for future JJVC research studies or disposed of at the mutual agreement of the Sponsor and Investigator.

If there is a discrepancy between the shipment documents and the contents, contact the study monitor immediately.

Clinical Study Protocol

Johnson & Johnson Vision Care, Inc.

7. STUDY EVALUATIONS

7.1. Time and Event Schedule

Table 3: Time and Events

Visit Information	Visit 1 Screening, Baseline, Treatment 1 Lens Fitting	Visit 2 Treatment 1 Follow-up/ Treatment 2 Lens Fitting	Visit 3 Treatment 2 Follow-up
Time Point	N/A	7 to 14 days from Visit 1	7 to 14 days from Visit 2
Estimated Visit Duration	2 hours	2 hours	1.5 hours
Statement of Informed Consent	x		
Demographics	x		
Medical History/Concomitant Medications	x	x	x
Habitual Contact Lens Information	x		
Inclusion/Exclusion Criteria	x		
Adverse event review	x	x	x
Subjective Sphero-Cylindrical Refraction	x		
LogMAR Visual Acuity	x	x	x
Slit Lamp Biomicroscopy	x	x	x
Corneal topography	x		
Lens application	x	x	
Over Refraction (with lenses)	x	x	
Lens Fit Assessment	x	x	x
DESMD tear film assessment	x	x	x
Dispense study lenses	x	x	
Exit LogMAR Visual acuity	x	x	x
Final Evaluation			x

7.2. Detailed Study Procedures

VISIT 1

It is preferred that subjects attend Visit 1 without their habitual contact lenses in situ. If possible, subjects should not wear lenses for 24 hours prior to the study visit in order to reduce the risk of biomicroscopy signs being a cause of ineligibility for the study.

Clinical Study Protocol

Johnson & Johnson Vision Care, Inc.

The visit can still go ahead if the subject is wearing their habitual lenses and it can take place at any time of the working day.

Visit 1: Screening			
Step	Procedure	Details	
1.1	Statement of Informed Consent	Each subject must read, understand, and sign the Statement of Informed Consent before being enrolled into the study. The Principal Investigator or his/her designee conducting the informed consent discussion must also sign the consent form. NOTE: The subject must be provided a signed copy of this document.	
1.2	Demographics	Record the subject's date of birth, gender, race and ethnicity.	
1.3	Medical History and Concomitant Medications	Questions regarding the subjects' medical history and concomitant medications.	
1.4	Habitual Contact Lens Information	Questions regarding the subject's habitual lens type and parameters.	
1.5	Habitual Contact Lens Wear Schedule	Record the duration of wearing this contact lens type and power (number of years and months). During the past 4 weeks, what is the minimum number of days per week that the subject has worn their lenses for at least 8 hours.	
1.6	Subject Information	In the subject's opinion, what is the average number of hours per day that they are looking at digital displays (eg. computer screen, phone, tablet). In the subject's opinion, what is the average number of hours per day (while awake) that they spend in an air conditioned environment.	

Clinical Study Protocol

Johnson & Johnson Vision Care, Inc.

Visit 1: Screening			
Step	Procedure	Details	[REDACTED]
1.7	Eligibility after Screening	
All responses to Screening Inclusion Criteria questions must be answered “yes” and all responses to Exclusion Criteria must be answered “no” for the subject to be considered eligible.
 
If subject is deemed to be ineligible after screening, proceed to Final Evaluation and complete Subject Disposition. Refraction and Biomicroscopy forms are not required.
	[REDACTED]

Visit 1: Baseline			
Step	Procedure	Details	[REDACTED]
1.8	Subjective Sphero-cylindrical Refraction	Subjective sphero-cylindrical refraction will be performed on both eyes.	[REDACTED]
1.9	Entrance LogMAR Visual Acuity	Distance high contrast visual acuity will be measured OD, OS and OU with the subjective refraction in place.	Appendix E: Eurolens Research SOP # 12A
1.10	Slit Lamp Biomicroscopy	
Grades will be scored to the nearest 0.1 in the best judgment of the investigator using Efron Grading Scales.
 
If any slit lamp findings are Efron Grade 3 or greater (e.g., corneal edema, corneal neovascularization, tarsal abnormalities, conjunctival injection), the subject may not continue at this time, but may return up to one additional time to determine eligibility. If discontinued a final examination must be completed.
 
If the clearance of the fluorescein needs to be expedited, preservative-free rewetting drops or saline may be instilled.
	Appendix F: Eurolens Research SOP # 13
1.11	Corneal topography	Corneal topography using the Medmont topographer will be carried out on each eye. Simulated K readings (mm) will be documented.	Eurolens Research SOP # 16

Clinical Study Protocol

Johnson & Johnson Vision Care, Inc.

Visit 1: Baseline			
Step	Procedure	Details	
1.12	DESMD environmental conditions	Record the room temperature and humidity	Appendix G
1.13	DESMD system tear film measurements (extended eye opening) without study contact lenses	
Pre-corneal tear film stability will be assessed using the DESMD system during a period of extended eye opening. Subjects will be asked to keep their left eye open for as long as they can (maximum of 30 seconds), with the subject's right eye occluded during the test. Tear film stability will be assessed on three occasions with a 5-minute break between measurements.
 
If the median pre-corneal tear film break-up time is less than 5 seconds, the subject is not eligible to continue in the study.
	Appendix G
1.14	Eligibility after Baseline	
All responses to Inclusion Criteria questions must be answered "yes" and all responses to Exclusion Criteria questions must be answered "no" for the subject to be considered eligible.
 
If subject is deemed to be ineligible after baseline, proceed to Final Evaluation and complete all forms.
	
1.15	Randomization	Subjects will be randomized to follow one of two possible lens wear sequences.	

Visit 1: Treatment 1 Lens Fitting			
Step	Procedure	Details	
1.16	Lens application	The first assigned lens type (as per the randomization table) will be applied to each eye. The first choice lens power will be determined based on the refraction findings and contact lens history at the investigator's discretion. BVP and lot number will be recorded. If a lens is damaged, a Product Quality Complaint Form will be completed. The lens will be stored in a labeled vial with unpreserved saline and clearly differentiated from any other lenses.	

Clinical Study Protocol
Johnson & Johnson Vision Care, Inc.

Visit 1: Treatment 1 Lens Fitting			
Step	Procedure	Details	[REDACTED]
1.17	Lens Settling	Lenses will settle for approximately 5 minutes.	[REDACTED]
1.18	Lens Fit Assessment	
Evaluate lens centration, movement on blink, and push-up test for each eye.
 
An unacceptable fit is defined by one or more of the following criteria:
 
 • limbal exposure at primary gaze or with extreme eye movement • edge lift • excessive movement with blink in primary gaze • insufficient movement with blink in upgaze • insufficient movement in push-up test 
Note: if lens fit is unacceptable for either eye, the subject will be discontinued from the study.
	[REDACTED]
1.19	LogMAR visual acuity & over-refraction, with option for lens modification	
Distance high contrast visual acuity will be measured for each eye as well as binocularly before and after over-refraction.
 
The lens power of one or both lenses may be modified based on the over-refraction at the investigator's discretion. Up to TWO power modifications are allowed (repeat steps 1.15 to 1.18).
 
N.B Minimum acceptable logMAR VA is 0.20 in each eye.
	Appendix E: Eurolens Research SOP # 12A
1.20	Exit LogMAR Visual Acuity	Distance high contrast visual acuity will be measured OD, OS, and OU with the study lenses in place.	Appendix E: Eurolens Research SOP # 12A
1.21	Dispensing criteria	
The lens fit and VA must be acceptable in order for a subject to be dispensed lenses.
 
Minimum acceptable logMAR VA is 0.20 in each eye.
 
If subject is discontinued, proceed to Final Evaluation and complete all forms.
	[REDACTED]

Clinical Study Protocol
Johnson & Johnson Vision Care, Inc.

Visit 1: Treatment 1 Lens Fitting			
Step	Procedure	Details	
1.22	Dispense lenses	
The subject will be instructed to wear the lenses on a daily disposable basis and informed that no other contact lens types should be used until the next study visit. Subjects will be instructed to try to wear the study lenses for at least 8 hours per day on the days between today's visit and the scheduled follow-up visit. No more than 2 days of missed lens wear between visits is allowed.
 
A patient instruction guide will be issued. Subjects should also be instructed to return any unopened lenses to the investigator at the next visit. Subjects do not need to keep any worn lenses, but are asked to keep and return any lenses which are associated with a suspected product quality issue.
	
1.23	End of Visit 1 and Instructions	Subject are discharged and asked to return 7 to 14 days later for the next visit. On the day of the scheduled follow-up visit, they are asked to come to the visit wearing the study lenses, having worn them for a minimum of 6 hours that day.	

VISIT 2

Subjects will be asked to attend Visit 2 after having worn the lenses for a minimum of 6 hours.

Visit 2: Treatment 1 Follow-Up / Treatment 2 Lens Fitting			
Step	Procedure	Details	
2.1.	Adverse Events and Concomitant Medications Review	Review any changes to the subject's medical history or concomitant medications from the previous study visit. Record any changes and any adverse events.	
2.2.	Contact lens wear time	On the days between visits (ie. not including the day of fitting and day of follow-up) when contact lenses were worn, what was the average wearing time and comfortable wearing time per day?	

Clinical Study Protocol
Johnson & Johnson Vision Care, Inc.

Visit 2: Treatment 1 Follow-Up / Treatment 2 Lens Fitting			
Step	Procedure	Details	[REDACTED]
2.3.	Compliance	Confirm compliance with the prescribed wear schedule.	[REDACTED]
2.4.	Subject Reported Ocular Symptoms	Subjects will respond to a verbal open-ended symptoms questionnaire.	[REDACTED]
2.5.	Entrance LogMAR Visual Acuity	Distance high contrast visual acuity will be measured OD, OS, and OU with the study lenses in place	Appendix E: Eurolens Research SOP # 12A
2.6.	Patient Reported Outcomes	Subjects will complete the follow-up questionnaire (CLDEQ-8, MRD).	[REDACTED]
2.7.	Slit Lamp Biomicroscopy (white light only, with lenses in)	
Grades will be scored to the nearest 0.1 in the best judgment of the investigator using Efron Grading Scales.
 
If any slit lamp findings are Efron Grade 3 or greater (e.g., corneal edema, corneal neovascularization, tarsal abnormalities, conjunctival injection) or < Efron Grade 3, which in the investigator's opinion would contraindicate contact lens wear, the subject may not continue at this time. Document any Adverse Events as appropriate.
 
Please note: This will not include assessment with sodium fluorescein.
	Appendix F: Eurolens Research SOP # 13

Clinical Study Protocol
Johnson & Johnson Vision Care, Inc.

Visit 2: Treatment 1 Follow-Up / Treatment 2 Lens Fitting			
Step	Procedure	Details	
2.8.	Lens Fit Assessment	
Evaluate lens centration, movement on blink, and push-up test for each eye.
 
An unacceptable fit is defined by one or more of the following criteria:
 
 • limbal exposure at primary gaze or with extreme eye movement • edge lift • excessive movement with blink in primary gaze • insufficient movement with blink in upgaze • insufficient movement in push-up test 
Note: if lens fit is unacceptable for either eye, the subject will be discontinued from the study.
	
2.9.	DESMD environmental conditions	Record the room temperature and humidity	Appendix G
2.10.	DESMD system tear film measurements (extended eye opening) with study contact lenses	Pre-lens tear film stability will be assessed using the DESMD system over a period of extended eye opening. Subjects will be asked to keep their left eye open for as long as possible (maximum of 30 seconds), with the subject's right eye occluded during the test. Tear film stability (breakup time in seconds) will be assessed on three occasions with a 5-minute break between measurements.	Appendix G
2.11.	Lens removal	The contact lenses will be removed. Worn lenses may be discarded if there is no associated adverse event or product quality complaint.	

Clinical Study Protocol
Johnson & Johnson Vision Care, Inc.

Visit 2: Treatment 1 Follow-Up / Treatment 2 Lens Fitting			
Step	Procedure	Details	[REDACTED]
2.12.	Slit Lamp Biomicroscopy	
Grades will be scored to the nearest 0.1 in the best judgment of the investigator using Efron Grading Scales.
 
If any slit lamp findings are Efron Grade 3 or greater (e.g., corneal edema, corneal neovascularization, tarsal abnormalities, conjunctival injection), the visit may not continue at this time, but may continue following the resolution of a reported Adverse Event.
 
If the clearance of the fluorescein needs to be expedited, preservative-free rewetting drops or saline may be instilled.
	Appendix F: Eurolens Research SOP # 13
2.13.	Lens application	The second assigned lens type (as per the randomization table) will be applied to each eye. The first choice lens power will be determined based on the refraction findings and contact lens history at the investigator's discretion. BVP and lot number will be recorded. If a lens is damaged, a Product Quality Complaint Form will be completed. The lens will be stored in a labeled vial with unpreserved saline and clearly differentiated from any other lenses.	
2.14.	Lens Settling	Lenses will settle for approximately 5 minutes.	

Clinical Study Protocol
Johnson & Johnson Vision Care, Inc.

Visit 2: Treatment 1 Follow-Up / Treatment 2 Lens Fitting			
Step	Procedure	Details	
2.15.	Lens Fit Assessment	
Evaluate lens centration, movement on blink, and push-up test for each eye.
 
An unacceptable fit is defined by one or more of the following criteria:
 
 • limbal exposure at primary gaze or with extreme eye movement • edge lift • excessive movement with blink in primary gaze • insufficient movement with blink in upgaze • insufficient movement in push-up test 
Note: if lens fit is unacceptable for either eye, the subject will be discontinued from the study.
	
2.16.	LogMAR visual acuity & over-refraction, with option for lens modification	
Distance high contrast visual acuity will be measured for each eye as well as binocularly before and after over-refraction.
 
The lens power of one or both lenses may be modified based on the over-refraction at the investigator's discretion. Up to TWO power modifications are allowed (repeat steps 2.13 to 2.16).
 
N.B Minimum acceptable logMAR VA is 0.20 in each eye.
	Appendix E: EuroLens Research SOP # 12A
2.17.	Exit LogMAR Visual Acuity	Distance high contrast visual acuity will be measured OD, OS, and OU with the study lenses in place.	Appendix E: EuroLens Research SOP # 12A

Clinical Study Protocol
Johnson & Johnson Vision Care, Inc.

Visit 2: Treatment 1 Follow-Up / Treatment 2 Lens Fitting			
Step	Procedure	Details	
2.18.	Dispensing criteria	
The lens fit and VA must be acceptable in order for a subject to be dispensed lenses.
 
Minimum acceptable logMAR VA is 0.20 in each eye.
 
If subject is discontinued, proceed to Final Evaluation and complete all forms.
	
2.19.	Dispense lenses	
The subject will be instructed to wear the lenses on a daily disposable basis and informed that no other contact lens types should be used until the next study visit. Subjects will be instructed to try to wear the study lenses for at least 8 hours per day on the days between today's visit and the scheduled follow-up visit. No more than 2 days of missed lens wear between visits is allowed.
 
A patient instruction guide will be issued. Subjects should also be instructed to return any unopened lenses to the investigator at the next visit. Subjects do not need to keep any worn lenses, but are asked to keep and return any lenses which are associated with a suspected product quality issue.
	

Clinical Study Protocol
Johnson & Johnson Vision Care, Inc.

Visit 2: Treatment 1 Follow-Up / Treatment 2 Lens Fitting			
Step	Procedure	Details	
2.20.	End of Visit 2 and Instructions	
Subject is discharged and asked to return 7 to 14 days later for the next visit. On the day of the scheduled follow-up visit, they are asked to come to the visit wearing the study lenses, having worn them for a minimum of 6 hours that day.
 
Subject is asked to bring their spectacles or contact lenses with them to the next scheduled visit, as these will be used for exit acuity.
	

VISIT 3

Subjects will be asked to attend Visit 3 after having worn the study lenses for a minimum of 6 hours.

Visit 3: Treatment 2 Follow-Up			
Step	Procedure	Details	
3.1.	Adverse Events and Concomitant Medications Review	Review any changes to the subject's medical history or concomitant medications from the previous study visit. Record any changes and any adverse events.	
3.2.	Contact lens wear time	On the days between visits (ie. not including the day of fitting and day of follow-up) when contact lenses were worn, what was the average wearing time and comfortable wearing time per day?	
3.3.	Compliance	Confirm compliance with the prescribed wear schedule.	
3.4.	Subject Reported Ocular Symptoms	Subjects will respond to a verbal open-ended symptoms questionnaire.	
3.5.	Entrance LogMAR Visual Acuity	Distance high contrast visual acuity will be measured OD, OS, and OU with the study lenses in place	Appendix E: EuroLens Research SOP # 12A
3.6.	Patient Reported Outcomes	Subjects will complete the follow-up questionnaire (CLDEQ-8, MRD)..	

Clinical Study Protocol
Johnson & Johnson Vision Care, Inc.

Visit 3: Treatment 2 Follow-Up			
Step	Procedure	Details	[REDACTED]
3.7.	Slit Lamp Biomicroscopy (white light only, with lenses in)	
Grades will be scored to the nearest 0.1 in the best judgment of the investigator using Efron Grading Scales.
 
If any slit lamp findings are Efron Grade 3 or greater (e.g., corneal edema, corneal neovascularization, tarsal abnormalities, conjunctival injection) or < Efron Grade 3, which in the investigator's opinion would contraindicate contact lens wear, the subject may not continue at this time. Document any Adverse Events as appropriate.
 
Please note: This will not include assessment with sodium fluorescein.
	Appendix F: EuroLens Research SOP # 13
3.8.	Lens Fit Assessment	
Evaluate lens centration, movement on blink, and push-up test for each eye.
 
An unacceptable fit is defined by one or more of the following criteria:
 
 • limbal exposure at primary gaze or with extreme eye movement • edge lift • excessive movement with blink in primary gaze • insufficient movement with blink in upgaze • insufficient movement in push-up test 
Note: if lens fit is unacceptable for either eye, the subject will be discontinued from the study.
	[REDACTED]
3.9.	DESMD environmental conditions	Record the room temperature and humidity	Appendix G

Clinical Study Protocol

Johnson & Johnson Vision Care, Inc.

Visit 3: Treatment 2 Follow-Up			
Step	Procedure	Details	[REDACTED]
3.10.	DESMD system tear film measurements (extended eye opening) with study contact lenses	Pre-lens tear film stability will be assessed using the DESMD system over a period of extended eye opening. Subjects will be asked to keep their left eye open for as long as possible (maximum of 30 seconds), with the subject's right eye occluded during the test. Tear film stability (breakup time in seconds) will be assessed on three occasions with a 5-minute break between measurements.	Appendix G
3.11.	Lens removal	The contact lenses will be removed. Worn lenses may be discarded if there is no associated adverse event or product quality complaint.	

FINAL EVALUATION

The final evaluation will ordinarily take place immediately following the last scheduled follow-up visit per the study protocol. It may also take place at any point the subject discontinues the study or is terminated from the study.

Final Evaluation			
Step	Procedure	Details	[REDACTED]
F.1	Final Exam Form	Indicate if the subject completed the study successfully. If subject discontinued from the study, indicate the reason.	
F.2	Subjective Sphero-cylindrical Refraction	Subjective sphero-cylindrical refraction will be performed on both eyes.	[REDACTED]
F.3	Best corrected logMAR acuity	Distance high contrast visual acuity will be measured OD, OS and OU with the subjective refraction in place.	Appendix E: Eurolens Research SOP # 12A
F.4	Exit Slit Lamp Biomicroscopy	The Efron slit lamp classification will be used to grade the findings. Adverse events will be documented and followed for significant slit lamp findings.	Appendix F: Eurolens Research SOP # 13

Clinical Study Protocol

Johnson & Johnson Vision Care, Inc.

Final Evaluation			
Step	Procedure	Details	[REDACTED]
F.5	Exit Visual Acuity	Record distance high contrast LogMAR visual acuity (OD, OS, and OU) with the subject's own spectacle or contact lens correction in place.	Appendix E: Eurolens Research SOP # 12A

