4.3. Enrollment Target and Study Duration

Up to 16 subjects will be enrolled, with a target of 10 subjects successfully completing the study.

The study will last approximately 3 months. Once the informed consent has been signed the subject will be considered enrolled. Subjects who are discontinued prior to the final evaluation will be replaced. Study recruitment will cease once 10 subjects have completed all study visits.

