8. SUBJECTS COMPLETION/WITHDRAWAL

8.1. Completion Criteria

Subjects are considered to have completed the study if they:

- Provided informed consent.
- They are eligible.

Clinical Study Protocol

Johnson & Johnson Vision Care, Inc.

- Have completed all study visits.
- Have not withdrawn/discontinued from the study for any reason described in Section 8.2.

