8.2. Withdrawal/Discontinuation from the Study

A subject will be withdrawn from the study for any of the following reasons:

- Subject withdrawal of consent.
- Subject not compliant to protocol including use of non-study lenses or not reaching the required wear times.
- Subject lost to follow-up.
- Subject no longer meets eligibility criteria (e.g. the subject becomes pregnant).
- Subject develops significant or serious adverse events causing discontinuation of study lens wear (more than 7 days).
- Subjects who have experienced a Corneal Infiltrative Event (CIE).
- Investigator's clinical judgment regarding the subject safety reasons (that it is in the best interest of the subject to stop treatment).
- Subject missed two consecutive study visits.
- Subject not compliant with study lens wear schedule.
- Subject not successfully dispensed due to lack of efficacy and safety including poor vision, poor comfort, or unacceptable fit.

For discontinued subjects, the Investigator will:

- Complete the current visit (scheduled or unscheduled).
- Complete the Final Evaluation, indicating the reason that the subject was discontinued from the study.
- Record the spherocylindrical refraction with best corrected distance visual acuity.
- Collect used test article(s) (worn or brought to the visit) from the subject and discard them, unless otherwise stated in Section 7.2.
- Collect all unused test article(s) from the subject.
- Make arrangements for subject care, if needed, due to their study participation.

Additional subjects will be enrolled if a subject discontinues from the study prematurely.

In cases where a subject is lost to follow-up, every possible effort must be made to contact the subject and determine the reason for discontinuation/withdrawal. The measures taken to follow up must be documented including two written attempts and a certified letter (or equivalent) as the final attempt.

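### A fit failure with the first-worn lens removes the subject before the second lens is tried, so Period 2 fit rates are conditional on passing the first lens; the status of a Visit 3 failure is also unsettled

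*Combined protocol and SAP*

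**What the plan says.** Section 2.1 gives one objective, fit acceptance of each of the two lenses. Section 4.2 justifies the crossover by its removal of between-subject variability.

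Section 7.2 has four fit checks: 1.18 (first lens, dispensing), 2.8 (first lens, follow-up), 2.15 (second lens, dispensing) and 3.8 (second lens, follow-up). Each carries the same instruction: "Note: if lens fit is unacceptable for either eye, the subject will be discontinued from the study". Between the second and third checks comes step 2.13: "The second assigned lens type (as per the randomization table) will be applied to each eye". The dispensing criteria at 1.21 and 2.18 add: "If subject is discontinued, proceed to Final Evaluation and complete all forms".

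On completion and replacement:
- Section 4.3: "Subjects who are discontinued prior to the final evaluation will be replaced". It also closes recruitment when 10 subjects have completed every visit.
- Section 8.1 requires that completers "Have not withdrawn/discontinued from the study for any reason described in Section 8.2".
- Section 8.2 gives the fit-related reason as "Subject not successfully dispensed due to lack of efficacy and safety including poor vision, poor comfort, or unacceptable fit". It also tells the investigator to finish the visit in progress, and says "Additional subjects will be enrolled if a subject discontinues from the study prematurely".

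Section 14.5 tabulates the fit rate by visit and lens type in the safety population, which Section 14.3 defines as everyone given any test article. Section 14.9 rules out imputation.

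**The concern.** The primary outcome decides who is observed on the second lens. A subject whose first lens fits badly in one eye leaves with both eyes, and the other lens is never tried. At step 2.8 this happens although the first lens is removed at 2.11 in any case.

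Two things are at stake. First, a crossover gains its information from subjects assessed on both lenses, and the pairs lost here are exactly those in which one lens is known to have failed. Second, if an eye that is hard to fit with one lens tends to be hard to fit with the other, the second-lens group has been cleared of some difficult eyes and its acceptance rate is too high. Section 14.2 says the data may be used to design later trials, so an inflated rate could be carried forward.

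A separate question arises at 3.8. The subject has by then worn both lenses and attended every visit, yet is to be discontinued. Whether that subject counts towards the 10 completers is not settled.

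**Working it through.** **Plan's own figure.** The sample size is up to 16 enrolled for 10 completers, and Section 14.2 says it does not rest on a power calculation. It implies only that up to 1 − 10/16 = 37.5% may be lost. There is no fit rate to reproduce, so every rate below is an assumption.

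**Step order.** 1.18 → 2.8 → 2.11 (first lens removed) → 2.13 (second lens applied) → 2.15 → 3.8 → Final Evaluation. Two first-lens checks precede 2.13. No step offers the second lens to a subject who fails either.

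**Share never given the second lens.** Let q be the subject-level failure probability at each check, taken as independent between checks. The share is 1 − (1 − q)².

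| q | Never given second lens | Of 16 randomized |
|---|---|---|
| 1% | 2.0% | 0.3 |
| 2% | 4.0% | 0.6 |
| 5% | 9.8% | 1.6 |
| 10% | 19.0% | 3.0 |

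With unequal rates: acceptance of 95% at dispensing and 97% at follow-up gives 1 − 0.95 × 0.97 = 7.85%; 90% and 95% give 1 − 0.90 × 0.95 = 14.5%.

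**Selection effect, mixture model.** Assume 20% of subjects are hard to fit (40% failure with either lens) and 80% are not (2% failure).
- True acceptance: 1 − (0.2 × 0.4 + 0.8 × 0.02) = 90.4%.
- Hard-to-fit share after passing the first lens: 0.2 × 0.6 / 0.904 = 13.3%.
- Acceptance in that group: 1 − (0.1327 × 0.4 + 0.8673 × 0.02) = 93.0%, a shift of 2.6 points.

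**Selection effect, latent normal model.** Each lens has a marginal failure rate, the latent correlation is ρ, and there is one check per lens. P(second fails | first passed) = (p₂ − P(both fail)) / (1 − p₁).

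| True failure, both lenses | ρ = 0 | ρ = 0.5 | ρ = 0.8 |
|---|---|---|---|
| 10% | 10.0% | 7.5% | 4.9% |
| 5% | 5.0% | 4.0% | 2.7% |

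Acceptance is overstated by 0, 2.5 and 5.1 points in the first row, and by 0, 1.0 and 2.3 points in the second.

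**Between-lens difference.** With true failure of 20% and 10%, the rates in second-worn lenses are 16.5% and 6.1% (ρ = 0.5) or 13.4% and 2.6% (ρ = 0.8). The differences are 10.4 and 10.8 points against a true 10. Pooled over both periods with equal sequences, lens A's rate is [p_A + (1 − p_B) × P(A fails | B passed)] / (2 − p_B), and likewise for B. This gives 18.3% against 8.3% (ρ = 0.5) and 16.9% against 6.7% (ρ = 0.8), differences of 10.1 and 10.2 points before rounding of the rates.

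**Visit 3 status.** For non-completion: 3.8 precedes the Final Evaluation, so the replacement rule in 4.3 literally applies. For completion: 8.1 excludes only discontinuation for an 8.2 reason, the fit reason in 8.2 concerns dispensing, nothing is dispensed at Visit 3, and the visit in progress is still finished. With no other loss, the chance of passing is (1 − q)⁴ if a Visit 3 failure is a non-completer and (1 − q)³ if not. The binomial probability of at least 10 completers from 16 is then 98.2% against 99.6% at q = 5%, and 70.7% against 88.6% at q = 10%.

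**The case against.** The planned analysis already protects much of the result. The safety population keeps every failure at the visit where it occurs. Because the table is by visit, its Visit 1 row is the Period 1 dispensing rate for each lens, randomized and unselected. That stands, and it limits the problem to the Visit 3 row and the second-lens part of Visit 2.

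The size depends on assumptions. Entrants already wear daily disposable silicone hydrogel lenses and have at most 1.00 DC of astigmatism, so failures may be rare. The lenses share an 8.5 mm base curve and have similar diameters (14.3 and 14.1 mm), but differ in material. At zero correlation there is no bias in the rate. A shift of 2.6 points is also smaller than one subject in 16 (6.25 points). All this is fair. Even so, the lost pairs do not depend on correlation, and the plan does not mark which rows are conditional.

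Three stronger readings are tempting, and the documents do not support them:
- A reader might infer that the better-fitting lens is favoured in the comparison because it is screened more often by the other lens. In the calculation above the difference moves by less than one point.
- A reader might infer that the trial will report 100% acceptance in its completers whatever the truth. No fit analysis in completers or the Per-Protocol set is specified, and the inference also needs every Visit 3 failure to be a non-completer.
- A reader might take it as settled that a Visit 3 failure is replaced. Sections 8.1 and 8.2 allow the opposite reading.

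The duty to finish the current visit could also be read as carrying a step 2.8 failure on to 2.13, but that runs against the note at 2.8 and nothing says so.

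**Conclusion.** The concern holds in limited form. Second-worn-lens fit is observed only in subjects whose two eyes both passed the first lens at 1.18 and 2.8. This follows from the step order and needs no assumption. About 2% to 19% of subjects would never receive the second lens for failure rates of 1% to 10% per check.

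Overstatement of Period 2 acceptance needs positive correlation between lenses. In the scenarios shown with positive correlation it is about 1 to 5 points. The Visit 1 row is unaffected. No error rate or power is involved, since the study is descriptive. The consequence is for absolute rates, denominators and the completeness of the within-subject comparison.

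On Visit 3, the finding is that the passages conflict. The conflict affects completer and replacement counts, not who is selected for the second lens.

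**What to change.** Leave the dispensing criterion at 1.21 and 2.18 as it is. Reconcile the notes at 1.18, 2.8, 2.15 and 3.8 with the crossover objective and with Sections 4.3, 8.1 and 8.2, so that a recorded fit failure:
- is a primary-endpoint outcome for that lens;
- does not by itself cancel the planned fit assessment of the other lens (most simply at 2.8, where the first lens comes off at 2.11 anyway);
- does not by itself turn a subject who attended all visits into a replaced non-completer.

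The safety grounds for ending participation are not in question here. Tabulate any second-lens fitting that follows a Visit 1 failure as Period 2, so that the Visit 1 row stays unselected.

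If conduct cannot change, the report should label the Visit 1 rates as the only unselected ones, describe Period 2 rates as conditional on passing the first lens, and state how many subjects never received the second lens. The Visit 3 status still needs one stated reading.

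The cost is a short amendment. A few subjects stay for one more fitting, and the reported rates may be slightly less favourable. The reporting fallback needs no extra data.
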